- patients with a follow-up period of less than one month. This occurs when a patient dies within the same month of registering with a general practice within the CCG. A limitation of the derived data from the patient registration data available to the IAU is that it only allows us to determine the month within which a move or a death occurred (see section on Data derived from NHAIS, p.18). In these cases, both dates are set as the day of the extraction date on which the new address or death was recorded

- patients without a record of prior emergency or elective admission in the three-year pre-study period (defined in section on Pre-period, p.24). These will be excluded because prior hospital data are required to define baseline patient characteristics, in particular patient comorbidities
- patients referred to an ICT between mid-May and mid-June 2017.

The exclusion criterion relating to no prior admissions is likely to exclude some patients who were referred to the ICT. An analysis done by NEHF CCG found that 20% of patients referred to the ICTs by end of February 2017 had no admissions (emergency or elective) in the previous two years. By allowing a period of three years, it is hoped that the number of exclusions will be minimised, while not unduly identifying historic comorbidities that have since been resolved (see section on Pre-period, p. 24).

Patients who change general practice within the CCG will be considered to be assigned to the locality of the general practice at the start of the follow-up period. NEHF CCG has confirmed that there were only a few cases where patients who were referred to one ICT changed general practice and ICT team.

The intervention group will be identified using the pseudonymised list of patients referred to an ICT, supplied by NEHF CCG (see sections on Data from NEHF CCG (p. 19) and Exposure variable (p. 23). Patients referred to an ICT after the mid-May cut-off and before mid-June will be excluded from the intervention group as they will not have a follow-up period of at least one month. They will also be excluded from the potential control group, as they would have received the intervention within the study period. Any patients referred to ICTs after mid-June 2017 may be considered as potential controls for this study.

Sources of data

Secondary Uses Services national administrative data

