Length of stay following an emergency admission is defined as the number of nights spent in hospital, calculated as the difference in days between the date of discharge and the date of admission. An admission and discharge within the same day will result in a length of stay of zero days.²³ Average length of stay per person is calculated by adding a patient's emergency admission lengths of stay and dividing by the number of emergency admissions. Average length of stay was chosen as a primary endpoint over the related measure – the total number of hospital bed days. Although hospital bed days is one of the 'core metrics' used within NHS England for the New Care Models programme,²⁴ it may not adequately measure the effect of the ICTs, as this endpoint reflects the length of stay in hospital as well as the number of emergency admissions. The ICTs are trying to proactively identify patients, which may inflate the number of emergency admissions in the short term. These admissions are expected to be of shorter duration than if they had not been proactively identified. If the 'counterfactual', longer hospital stay in the control group only occurs after the end of the study period for some patients, the hospital bed days measure may not adequately reflect the changes, as no admission during the study period is equivalent to an admission with a zero length of stay. Hospital bed days are included as a secondary endpoint.

Secondary outcomes

Secondary outcomes, all calculated over the follow-up period, will be:

- number of emergency readmissions within 30 days of discharge, per patient
- number of elective admissions per patient

- number of outpatient appointments per patient (excluding 'did not attends', and defined using code Attended=5 or 6 in SUS)
- average length of stay following an elective admission per patient
- proportion of total emergency bed days per patient, relative to total number of days at risk (i.e. days in the follow-up period)
- proportion of total elective bed days per patient, relative to total number of days at risk (i.e. in the follow-up period)
- proportion of deaths outside of hospital (as proxy for dying in preferred place of death).

All count outcomes will be modelled allowing for varying study lengths, in the same way as for the primary outcomes described above.

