Appropriate baseline variables will be included in both the matching and the regression models. All baseline variables are calculated on pre-period data. Potential baseline variables to include in the matching or as covariates in the modelling are listed in Table 3.

Table 3. Potential baseline variables

Category	Variables at patient level
Demographics & socio-demographics	
 • Approximate age at index date • Gender • Ethnicity • Average socioeconomic deprivation deciles, based on the Index of Multiple Deprivation (IMD) 2015, available at layer super output area (LSOA) level • Urban/rural classification at lower LSOA level, based on the 2011 census
Prior hospital use	
 • Number of emergency admissions in the last 60 days of the pre-period • Number of emergency admissions in year -1, the last year of the pre-period (i.e. 365 to 1 day before index date) • Number of emergency admissions in year -2 of the pre-period (i.e. 730 to 366 days before index date) • Number of ACS emergency admissions in the last 60 days of the pre-period • Number of ACS emergency admissions in year -1 of the pre-period • Number of ACS admissions in the year -2 of the pre-period • Number of elective admissions in year -1 of the pre-period • Number of A&E attendances in year -1 of the pre-period • Number of outpatient attendances in year -1 of the pre-period • Number of missed outpatient visits in year -1 of the pre-period • Average length of stay in year -1 of the pre-period
Health variables	
 • Elixhauser list of comorbidities, identified in the pre-period • Specific comorbidities linked to frailty, identified in the pre-period³⁰ • Other comorbidities predictive of hospital emergency admission, as identified in the Inpatient Outpatient A&E and GP(IPOPAEGP) model,³¹ identified in the pre-period

	
 • Number of Elixhauser comorbidities in the pre-period • Number of frailty comorbidities in the pre-period
Support	
 • Resident in a nursing or residential home
Time period	
 • Index date/period (quarter & year, e.g. q1y1, q2y1...)
Level of care available	
 • Locality in which the patient is registered with a GP

All comorbidities will be defined using data from any diagnosis field in any hospital admission in the pre-period.

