Modelling options also included adjusting for only a list of 'core' variables and those variables considered most predictive of the outcome, as the low number of events for some of the outcomes may otherwise have led to over-parametrised models. The most predictive variables were identified by running a lasso regression and where possible included all core variables as a minimum.⁵⁷ Variables considered 'core' were: age; gender (male or not male); IMD quintile; locality; Charlson Index; number of Elixhauser comorbidities; number of frailty comorbidities; history of mental ill health; index date quarter; hospital use in year prior to index date; and emergency admissions, CACS emergency admissions and UCS emergency admissions in the two months prior to index date.

Due to low numbers of care home residents (<10) in both ICT and matched control groups, analyses only adjusted for whether patients lived at home or in a care home (i.e. no differentiation between nursing and residential homes).

Following the analysis, it was found that outpatient appointments included community data from Virgin Care Services that had been uploaded to SUS in error. These appointments were removed from the data and the analysis of outpatient hospital use was redone. Other outcomes were not reanalysed; therefore in the case where these analyses adjusted for outpatient appointments in the year prior to the study, this variable would have contained some community outpatient appointments from Virgin Care Services.

Modelling options did not include multilevel models with locality as a random effect, as five localities were considered too few groups to adequately run such a multilevel model.

Acknowledgements

We are grateful to the North East Hampshire and Farnham CCG team for their support and their review and feedback on an earlier version of this statistical analysis protocol. We are also grateful to [name] and [name] for their peer review comments on an earlier version.

References

- ¹ NEHF CCG. Happy, Healthy, at Home (accessed 29 June 2017). Available from: www.northeasthampshireandfarnhamccg.nhs.uk/about-the-ccg/happy-healthy-at-home
- ² Moran P. Short Stay Emergency Admissions. NEHF CCG, available on request. 2016.

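### Table 3 has no prior-year value for three secondary outcomes (emergency bed days, elective bed days, 30-day readmissions), so imbalance in them would go unseen

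*Protocol*

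**What the plan says.** The secondary outcomes (Protocol, section 2, Study endpoints) include "proportion of total emergency bed days per patient, relative to total number of days at risk", "proportion of total elective bed days per patient, relative to total number of days at risk" and "number of emergency readmissions within 30 days of discharge, per patient".

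On baseline data, the same section says: "Potential baseline variables to include in the matching or as covariates in the modelling are listed in Table 3". Under prior hospital use, Table 3 gives emergency and ACS emergency admissions (last 60 days, year -1, year -2), "Number of elective admissions in year -1 of the pre-period", A&E attendances, outpatient attendances and missed outpatient visits in year -1, and "Average length of stay in year -1 of the pre-period". It does not list prior nights in hospital, emergency or elective, or prior readmissions.

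Diagnostics says that balance is judged on the variables in the Baseline variables section. Baseline variables and Choice of matching variables say that covariates are ranked by how well they predict emergency admissions. Statistical analysis lets the adjusted model take in further covariates that predict the outcome. The Addendum (section 5) adds mental ill health variables to the baseline set. It defines a core covariate list that includes prior-year hospital use, not itemised, and "emergency admissions, CACS emergency admissions and UCS emergency admissions in the two months prior to index date". It does not add prior nights or readmissions.

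**The concern.** The plan gives most of its utilisation outcomes a baseline counterpart, and three are left without one. In a matched study whose main stated threat is confounding, the prior value of an outcome is the natural first check of comparability and often its best predictor. If it is neither derived nor tabulated, the groups may have started from different levels of bed use or readmission, and that difference would be read as an effect of the integrated care teams (ICTs). This part of the confounding is observable in data already held. Some precision is also at stake, in a study that describes its sample of about 900 as possibly too small.

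**Working it through.** The plan states no precision or power figure, so there is none to reproduce.

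**1. Outcomes against baseline counterparts (Study endpoints against Table 3)**

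| Outcome | Prior value in Table 3 |
|---|---|
| Emergency admissions | 60 days, year -1, year -2 |
| Chronic ACS and urgent care sensitive admissions | ACS admissions: 60 days, year -1, year -2 |
| A&E, outpatient, elective admissions | year -1 |
| Average stay, emergency or elective | average stay in year -1, admission type not stated |
| 30-day emergency readmissions | none |
| Emergency bed days | none |
| Elective bed days | none |
| Deaths outside hospital | not applicable |

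**2. Can listed variables stand in?**

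- Emergency nights: largely. Admissions multiplied by average stay gives approximate nights if the average covers emergency stays. The product is not itself a listed covariate. The Addendum also ignores overlapping spells for average stay but counts unique days for bed days.
- Elective nights: weakly. The Addendum counts day cases as elective admissions, and these contribute no nights.
- Readmissions: partly, through the emergency admission counts. The documents give no figure for how much.

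**3. Why days must lie before the index date.** The Addendum assigns a spell that crosses the index date wholly to the pre-period when computing baseline average stay. Nights after the index date then enter a baseline variable. New counts should not repeat this.

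**4. Precision for emergency bed days.** Every input here is an assumption: gamma-Poisson admissions with mean 1.2 a year, mean stay 5 or 6 nights, and between-patient SD of log stay from 0.3 to 0.9 (up to 1.0 in the R² check). The quantity is the cut in standard error (SE) from adding prior-year emergency nights.

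- 720 per group, model with prior-year admissions and average stay, nights added as log(1 + nights), 250 replicates. The SD of the log bed-day ratio falls from 0.112 to 0.108, 0.129 to 0.122 and 0.155 to 0.142. The cuts are 1 - 0.108/0.112 = 4%, 1 - 0.122/0.129 = 5% and 1 - 0.142/0.155 = 8%.
- Log-link model with 1 to 23 months of follow-up, and with year -2 and elective admissions included (200 replicates): 3%, 3% and 8%.
- Inputs of the first item, gamma shape 1, 400 replicates: 1.4%, 2.1% and 2.5% with linear listed covariates; 0.3%, 0.6% and 0.9% when these are log-scaled and year -2 admissions are added.
- A further 400 replicates with year -2 and elective admissions included: about 2% to 8% with linear listed covariates, about 0% to 2% with log-scaled ones, and nothing when nights enter linearly.
- R² for log(1 + nights) in 200,000 simulated patients, SE cut = 1 - √[(1 - R² with)/(1 - R² without)]: from 0.01% to 1 - √(0.8021/0.8255) = 1.4%.

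Together these span roughly 0% to 8%. For scale, a covariate with partial correlation ρ multiplies the variance by 1 - ρ². With ρ = 0.2 the SE falls by 2.0% and 900 patients act like 900/0.96 = 938. With ρ = 0.4 it falls by 8.3% and they act like 900/0.84 = 1,071.

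**5. Patients with no admission in year -1.** Average stay is a sum divided by a count, so it has no value for them. Entry requires an admission in three years, not in the last one. The only figure is that "20% of patients referred to the ICTs by end of February 2017 had no admissions (emergency or elective) in the previous two years". It covers two years and all referred patients, before the three-year exclusion, so the share must be modelled. With gamma frailty of shape k, P(none in t years) = (1 + mt/k)^(-k), and m is set so that P(none in 2) = 0.20. The share among eligible patients is [P(1) - P(3)]/[1 - P(3)]:

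- k = 0.5: (0.277 - 0.164)/(1 - 0.164) = 13.5%
- Poisson limit: (0.447 - 0.089)/(1 - 0.089) = 39.3%

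A direct grid, with 2% to 10% of referred patients admitted only in year -3 and 5% to 25% admitted in year -2 but not year -1, runs from 0.07/0.82 = 9% to 0.35/0.90 = 39%.

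**The case against.** The strongest reply is that the list is open. Table 3 holds potential variables, the adjusted model may take any further predictor, and the Addendum makes prior-year hospital use core and selects predictors by lasso. Prior nights are also close to the product of two listed variables, so adding them invites the collinearity and over-parametrisation that the plan warns about. Much of this stands. It explains why the precision gain is small, and it is a reason not to put all the new variables into every model. It does not meet the balance point: the check covers listed variables, lasso can select only what was derived, and nothing in the text shows that nights or readmissions were.

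Two stronger readings are tempting but not supported.

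- A reader might infer that patients with no year -1 admission are dropped or miscoded. No passage says so. The Addendum's extra exclusions concern missing area codes and control age, and the plan expects all intervention patients to be matched. Coding them zero is workable, because year -1 admission counts in Table 3 separate them from patients with only same-day stays. The unstated coding rule is a detail that a protocol may leave to later documents.
- A reader might infer that urgent care sensitive admissions, a primary outcome, lack a prior-year value. Study endpoints treats chronic and urgent care sensitive conditions together as ACS definitions, so Table 3's ACS counts can be read as covering both, and prior-year hospital use is core.

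**Conclusion.** The point holds for three secondary outcomes. Table 3 has no prior-year emergency nights, elective nights or 30-day readmissions, and the stated balance check would not reveal a difference in them. Among outcomes with a natural prior value, the gap is confined to these three; the primary outcomes are not affected.

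A reader might also infer that the omission throws away substantial free precision. The calculations do not show that. For emergency bed days the gain is roughly 0% to 8% of the SE. It lies near the top only with wide between-patient variation in stay and linear listed covariates, and near zero when those covariates are already log-scaled. All of this rests on assumed distributions. For elective bed days and readmissions the gain is not quantified, because the documents give no correlation. The case for the change is balance checking and confounding control. The share of eligible patients who would need the no-admission indicator, about 9% to 39%, is likewise an assumption-based range.

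**What to change.** - Derive three year -1 values from SUS data, using only days before the index date: emergency nights, elective nights and 30-day emergency readmissions. Zero is a true value for each.
- Add them to Table 3 and to the balance table, with standardised differences before and after matching.
- Adjust each of the three outcomes for its own prior value, for example as log(1 + x), rather than adding all three to every model.
- Where baseline average stay is used, code patients with no year -1 admission as zero and add a no-admission indicator.

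Cost: three derived counts and a rerun of the balance table and the affected models, with no new data. Downside: one or two extra covariates in each affected model, correlated with those already there. The planned collinearity checks should cover them.

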- If the patient was not referred to the ICT (i.e. in the potential control group), then monthly potential index dates will be assigned, starting from the latest of the following:
 - the study period start date (see section on Bedding-in period and study period, p. 23)
 - date of earliest registration with a general practice in NEHF CCG, set as the date of the extraction in which they are first known to have been registered with a general practice in NEHF.

If a patient was referred more than once, only the first date is used, that is, if patients were discharged and then subsequently referred again, they are treated as though they stayed on the ICT register. No differentiation will be made between active or dormant patients (see section on Integrated care teams, p. 12).

For potential control patients, monthly index dates will be assigned from mid-July 2015 up to mid-May 2017. As the first and last monthly dates may be based on extraction dates (see

above and below), the dates set for all other months will for consistency also correspond to the extraction date of the corresponding month. This will also enable more accurate information on whether a patient was a care home resident at the index date, which is one of the potential covariates (see section on Baseline variables, p. 25).

A person's follow-up period ends when the person either dies, moves from NEHF CCG or the study period ends. Thus, the end date is defined as the earliest of the following dates:

- the end of the study period, that is mid-June 2017, set to the date of the last available NHAIS extract
- date of death, set to the date of the extraction in which death is first recorded
- date of de-registration from CCG general practice, set to the day before the date of the extraction in which they were first registered with a general practice outside NEHF.

A person's follow-up period may therefore be between approximately 1 and 23 months.

The date of death is estimated as the extraction date of when they were first recorded as having died. However, as the true death date could be as early as the day after the previous extraction date, there is a risk that the follow-up period is overestimated by up to a month, during which time the patient would have no recorded hospital activity. However, as it is unlikely that the day of the month that a person dies is other than random, this is unlikely to introduce bias between the intervention and control groups.

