Matching will be done without replacement if possible (i.e. each intervention patient will be matched to a unique patient in the control group). If, however, it is difficult to find balanced groups, matching will be done with replacement, that is, the same control patient can be matched to several intervention patients. Additionally, as a same potential control patient will be assigned monthly index dates, the same control patient may also be matched to several intervention patients, but with different index dates (and correspondingly potentially slightly

different baseline characteristics). The IAU will match 1:1, that is, one control patient to each intervention patient.

The genetic matching algorithm will try various distance functions to determine the 'closeness' of the match. However, for some variables a match may be required to be exact or to fall within a pre-fixed 'caliper', whereby the variables are required to be within a fixed distance of one another. Table 4 shows those variables where special matching methods are to be applied.

Table 4. Matching variables and method of matching

Variable	Method of matching
Living at home, in a nursing home or in a residential care home	Exact

The IAU will match within each locality separately to ensure that the intervention patients have access to the same PACS services as their control patients and ensure balance within each locality.

It is expected that all intervention patients will be matched to controls.

As the IAU is not matching on length of time in the study (as this could be correlated with quality of care), the intervention and their control patients may differ in this respect. The IAU will conduct descriptive analyses regarding length of time in the study, and address differences using an offset in the model which will allow for differences in time at risk.

Choice of matching variables

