The IAU aims to estimate the average treatment effect for the treated (ATT). Once matched controls have been selected, the IAU will estimate the effect of ICTs on the intervention group compared with the control group by fitting multivariable regression models, both unadjusted and adjusted for covariates. The adjusted model will contain all variables that were used in the matching process to adjust for any remaining observed imbalance, as well as any other covariates predictive of outcome. Index date will be included as a quarter/year categorical variable. Modelling checks for collinearity will be carried out and, if appropriate, the list of covariates will be changed accordingly.

Explored modelling options will include multilevel models with locality as a random effect, to capture any between-locality heterogeneity in outcomes. An additional advantage of a random effect modelling approach lies in obtaining more precise local estimates in the event of issues with data sparsity from particular localities.

Each outcome will be analysed by fitting a regression model that is appropriate to the type of outcome and the distributional properties of the data.

The count variable endpoints, such as number of emergency admissions per patient, will be analysed using a generalised linear model suitable for count data, such as a Poisson, to estimate the rate ratio between intervention and matched control patients. The effect of the intervention on the absolute (as opposed to relative) number of events (e.g. admissions) will also be estimated.

Model fit will be assessed by examining diagnostic statistics and over-dispersion parameters (e.g. the ratio of the residual deviance to the residual degrees of freedom), and excess zeros by comparing predicted and observed proportion of zero counts. If over-dispersion is detected then an alternative model, such as a negative binomial or the zero-inflated Poisson for count data, will be fitted. Where a similarly good fit is obtained using multiple models, a choice will be made by comparing the log-likelihood ratio and the Akaike information criterion (AIC), as appropriate. The appropriateness of the random effect assumption on locality will be assessed through formal statistical checks (like the intraclass correlation coefficient) and comparison with the corresponding fixed effect model.

As a guide, Table 6 details the typical regression models and alternatives for each outcome.

Table 6. Regression models for each outcome

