The IAU identified a number of ‘overlapping’ in-patient spells (stays) in the SUS data where, for example, a patient spell with one provider did not end before a spell with another provider started. When calculating average length of stay, we did not account for these overlapping spells. Instead, the average length of stay was calculated for each spell, as recorded in the data. Note: For the outcomes emergency bed days and elective bed days, bed days were not double-counted, that is the number of unique days in hospital following either emergency or elective admission were calculated.

Duplicate outpatient appointments were removed. Outpatient appointments relating to mental health services, to the extent these were recorded in the outpatient data, were included.

Index dates and follow-up, page 24

To further limit the size of the dataset of potential controls, only one potential index date per quarter was created for potential patients aged less than 65 years. Only 14% of ICT patients in the study were younger than 65 years.

Baseline variables, page 26

The variables mental ill health and serious mental ill health, as defined on page 32, were included as baseline variables, replacing the mental health definition specified in IPOPAEGP.

Connective tissue disease in the IPOPAEGP was not included as a baseline characteristic, as it overlapped with the Elixhauser definition of rheumatic arthritis. The Elixhauser variable peripheral vascular disorders was not included in error.

Identifying control group, page 28

Due to low numbers of care home residents that were referred to ICTs (<10), matching on type of residence (ie whether a person lived at home, in a nursing or a residential care home) was not done by exact matching.

Matching parameters, page 29

Due to the size of the dataset of potential control patients (approximately 750,000 records), the parameters for the genetic matching algorithm was limited to iterations based on population size 200, maximum generation 100 and number of generations to wait 10.

Statistical analysis, page 30

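### Control people may be reused at several index dates, and the models named make no allowance for it, so confidence intervals and p values are too narrow to the extent that reuse occurs

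*Protocol*

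**What the plan says.** Under Identifying control group the Protocol begins with "Matching will be done without replacement if possible" and explains this as meaning that "each intervention patient will be matched to a unique patient in the control group". If balance is hard to reach, the fallback is that "matching will be done with replacement, that is, the same control patient can be matched to several intervention patients". A further sentence, introduced as an addition to that fallback, says that because potential controls carry monthly index dates, "the same control patient may also be matched to several intervention patients, but with different index dates". Table 5 lists control sampling as without replacement, with one control per intervention patient.

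Under Index dates and follow-up period, for potential controls, "monthly index dates will be assigned from mid-July 2015 up to mid-May 2017". Follow-up ends at the earliest of death, de-registration or the end of the study period in mid-June 2017.

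Under Statistical analysis, a count endpoint "will be analysed using a generalised linear model suitable for count data, such as a Poisson". Table 6 adds negative binomial and zero-inflated Poisson as alternatives for counts, and binomial, quasi-binomial or negative binomial models for proportions. The only grouping considered is locality, as a random effect, and the addendum says that this was not used.

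The addendum also says that "only one potential index date per quarter was created for potential patients aged less than 65 years", in order to limit the size of the dataset, and gives the pool of potential controls as "approximately 750,000 records". It changes the search settings in Table 5 but not the sampling method, and it does not say whether the fallback was used.

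**The concern.** The matching pool consists of person-index-date records. Sampling records without replacement stops one record from being drawn twice. It does not stop one person from being drawn at two dates, and the section says openly that this may happen. The explanation that each intervention patient gets a unique control patient does not fit that sentence.

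Two rows from one person are not two independent observations. They share an end date, so the later follow-up lies wholly inside the earlier one, and every admission in the later window is counted in both. A variance computed as if the rows came from different people overstates the information in the control arm. The rate ratios and odds ratios, with their 95% intervals and p values, are what the Reporting section says will be presented. The mortality comparison under Sensitivity analyses is touched as well, because a reused person's death counts once per row.

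**Working it through.** The Protocol gives no sample size calculation, standard error or reuse rate, so there is no stated figure to reproduce.

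**Inputs from the Protocol.** About 900 intervention patients (Statistical conclusion validity); 1:1 matching; index dates from mid-July 2015 to mid-May 2017, which is 23 monthly dates; follow-up of 1 to 23 months; 95% intervals. Two-sided testing, the reuse share, the number of uses and the within-person correlation are assumptions.

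**Step 1: how strongly rows from one person correlate.** For Poisson counts at a constant rate, nested windows of lengths T1 > T2 have correlation √(T2/T1).
- 23 and 22 months: √(22/23) = 0.98.
- 2 and 1 months: √(1/2) = 0.71.
- 23 and 1 months: √(1/23) = 0.21.

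Differences between people in their underlying rate push these values up. A range of 0.5 to 1 is reasonable for illustration, with 1 as the upper limit.

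**Step 2: from reuse to type I error.** Let a share q of control rows come from people used m times, with correlation ρ.
- Control-arm design effect: D = 1 + q(m − 1)ρ.
- True SE / model SE, equal arms: √((1 + D)/2).
- Actual type I error: 2[1 − Φ(1.96 / √((1 + D)/2))].

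| Reuse among control rows | ρ | D | SE ratio | Type I error |
|---|---|---|---|---|
| None | any | 1.00 | 1.000 | 5.0% |
| 20% from people used twice | 0.5 | 1.10 | 1.025 | 5.6% |
| | 0.9 | 1.18 | 1.044 | 6.1% |
| | 1 | 1.20 | 1.049 | 6.2% |
| 50% from people used twice | 0.5 | 1.25 | 1.061 | 6.5% |
| | 0.9 | 1.45 | 1.107 | 7.7% |
| | 1 | 1.50 | 1.118 | 8.0% |

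**Step 3: simulation.** Each scenario had 1,500 runs, 900 rows per arm, random monthly index dates, a common end at month 23 and no true effect. One event per person-year and a gamma frailty variance of 1 were assumed. A negative binomial model with a log-time offset was fitted, first with the model-based SE and then with the SE clustered on person.

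| Reuse | Empirical SE | Model SE | Clustered SE | Type I, model | Type I, clustered |
|---|---|---|---|---|---|
| None | 0.069 | 0.070 | 0.070 | 3.9% | 4.0% |
| 20% twice | 0.072 | 0.070 | 0.073 | 6.1% | 4.9% |
| 50% twice | 0.077 | 0.070 | 0.076 | 7.7% | 4.7% |

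Monte Carlo error is about √(0.05 × 0.95 / 1,500) = 0.6 percentage points. The model SE does not move as reuse rises, while the clustered SE follows the empirical one.

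**Step 4: what the pool size suggests.** At no more than 23 records each, 750,000 records imply at least 750,000 / 23 ≈ 32,600 people. If the 900 rows were drawn at random, a row would share its person with 899 / 32,600 = 0.028 other rows on average. At ρ = 1, D = 1.028 and type I error is about 5.2%. Matching is not random. If the usable pool were ten times smaller, the figure would be 899 / 3,260 = 0.276 other rows, and type I error about 5.8% (ρ = 0.5) to 6.6% (ρ = 1). D = 1.5, and hence 8.0%, needs a usable pool of about 899 / 0.5 ≈ 1,800 people at ρ = 1, some 18 times smaller than 32,600.

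**The case against.** The strongest reply is that this is a risk and not a demonstrated error. The reuse sentence says only that it may happen, and it discloses the practice. The pool is large for about 900 matches, and index dates can be up to 22 months apart, so heavy reuse of near-identical rows is not shown. Analysing matched pairs without the pairing tends to make unadjusted standard errors too large, which works the other way. The Protocol already warns that even significant results need caution because of unobserved confounding.

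Most of this stands as a limit on size. A reader might infer that every reported interval is certainly too narrow, or that type I error has reached 8% or more. The documents support neither, because no reuse rate is given and the offset from pairing is unquantified. A reader might also infer that the plan promised a unique person for each match and broke that promise. It did not: the sentence is qualified by the words if possible. Nor does the Protocol say that rows are treated as independent. That follows from the models named and the absence of any person-level term, and Table 6 is offered as a guide.

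What does not stand is that the existing safeguards cover the problem. Over-dispersion checks address the spread of counts across rows, not duplicated people. The quarterly index dates apply only below age 65, and the addendum says that only 14% of ICT patients in the study were that young. The warning on confounding concerns a different source of uncertainty.

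**Conclusion.** The point holds in conditional form. Reuse of a control person is expressly allowed, reused rows overlap by construction, and nothing in the Protocol or its addendum allows for it in the variance. The understatement is nil without reuse, about 0.6 to 1.2 percentage points of type I error if 20% of control rows come from people used twice, and about 1.5 to 3 points if half do. These sizes rest on an assumed correlation of 0.5 to 1, two-sided 5% testing and equal arms, and leave out the pairing. The pool size makes the lower end more plausible than the upper, but cannot settle it. The number of unique control people is not among the listed reporting requirements, so a reader may not be able to tell whether any interval is affected. This should be fixed, but it does not by itself overturn the study's conclusions.

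**What to change.** - Compute the variance in every outcome model clustered on the pseudonymised patient ID, or bootstrap by person. Treat the mortality and Kaplan-Meier comparison in the same way.
- Report the number of unique control people and how many were used once, twice or more often, and say whether the with-replacement fallback was used.
- Reconcile the explanation of matching without replacement and the Table 5 entry with the reuse sentence, so that it is clear that the unit is the record.

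The patient ID already links the data sources, so no new data are needed. The addendum describes analyses already done, so the cost is a re-run of the fitted models, with intervals slightly wider where reuse occurred. Limiting each control person to one index date is optional and would mean repeating the matching; clustering does not require it.
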